9.1 Data Collection Procedures

- Standardized assessment forms completed by parents/caregivers
- GAS observations recorded by trained research team members
- Weekly scoring reviewed by occupational therapy leads for reliability
- Data entry into secure database by participant number

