2.1 Primary Objectives

Child Participants (Aim 1):

1. To examine the effects of the Building Resilience Program (BRP) on coping skills, engagement, self-regulation, emotional health, quality of life, and stress in preschool participants aged 24-66 months with history of ACEs
2. To evaluate the effectiveness of Goal Attainment Scaling (GAS) as a measurement tool for tracking individual progress and changes pre-post intervention

Caregiver Participants (Aim 2):

3. To examine the effects of the Building Resilience Program on caregiver resilience, emotional management, and coping strategies
4. To assess caregiver satisfaction with program methods and outcomes

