6.3 Caregiver Intervention Component

Duration: 3 caregiver-only sessions and one joint child-caregiver sessions over 8-week period (reduced from weekly caregiver sessions to accommodate participation challenges) **Format:** In-person group sessions **Staffing:** Occupational therapists and occupational therapy students

6.3.1 Caregiver Session Schedule:

1. **Pre-intervention meeting:** BRP and study description, introduction to resilience, highlights from Inside Out movie, Zones of Regulation overview, Q&A
2. **Week 3 session:** Family resilience, high vs. low resilience, resiliency BINGO activity, Kawa River model, Q&A
3. **Week 6 session:** Adaptive vs. maladaptive behaviors, coping strategies, mindfulness, sensory processing and "sensory solutions," community resources
4. **Post-intervention meeting:** Child and self-advocacy, joint plant activity, program review

6.3.2 Participation Requirements:

- Caregivers attend sessions during their child's intervention period only
- Both post-intervention periods required for complete assessment battery
- Attendance at weeks 3 and 6 sessions only when child participating in BRP intervention

7. Outcome Measures

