7.1 Primary Outcome Measures

7.1.1 Standardized Assessment Battery

NIH Toolbox Parent Report Emotion Measures:

- Negative Affect subdomain (anger, fear, sadness/depression)
- Psychological Well-being subdomain (positive affect, life satisfaction)

PROMIS Early Childhood Measures:

- Flexibility
- Persistence (Note: Curiosity and Frustration Tolerance removed due to ceiling effects)

Pediatric Quality of Life Inventory (PedsQL):

- Physical Functioning
- Emotional Functioning
- Social Functioning
- School Functioning

- Composite Score

Canadian Occupational Performance Measure (COPM):

- Parent proxy report of child's occupational performance
- Used primarily for Goal Attainment Scaling development

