11.3 Data Monitoring

- Weekly review of attendance and assessment completion
- Monthly data quality checks ([name] and [name])
- Progress reports to funding agencies as required (midterm and final to AOTF)

12. Adverse Event Reporting

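### The week-7 difference on the caregiver-completed measures cannot be separated from a change in how IG1 caregivers rate

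*Combined protocol and SAP*

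**What the plan says.** **Who rates.** Section 9.1 lists "Standardized assessment forms completed by parents/caregivers" and names no exception. Section 7.1.1 is consistent with this: it heads one block "NIH Toolbox Parent Report Emotion Measures" and describes the COPM as "Parent proxy report of child's occupational performance". No section describes masked caregivers or an independent informant for these measures.

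**Who is taught.** Section 6.3.2 states "Caregivers attend sessions during their child's intervention period only" and "Attendance at weeks 3 and 6 sessions only when child participating in BRP intervention". Under 4.2, IG2 children do not start the BRP until Phase 2.

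**What is taught.** Under 6.3.1 the week 3 session deals with family resilience and with high versus low resilience. The week 6 session is listed as "Adaptive vs. maladaptive behaviors, coping strategies, mindfulness, sensory processing and 'sensory solutions,' community resources".

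**What is tested and concluded.** The first objective in 2.1 begins "To examine the effects of the Building Resilience Program (BRP) on coping skills, engagement, self-regulation". Section 8.2.1 tests it with an ANCOVA of week-7 standardized scores, IG1 against IG2, adjusted for baseline. Section 2.2 expects the children to improve as shown by the standardized assessments and GAS. Caregiver resilience, emotional management and coping form a separate Aim 2.

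**The concern.** The person who completes the outcome form is also a recipient of the programme, and at the time of the primary comparison this is so in one arm only. A caregiver who has just been taught about coping and about adaptive and maladaptive behavior may rate the same behavior differently. Ratings could improve through expectation or worsen through closer noticing. If Aim 2 succeeds, the instrument used for Aim 1 may have changed in IG1 and not in IG2.

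This differs from the attention the children receive. The control condition in 6.2 is meant to balance researcher contact with the child, and it has no caregiver counterpart. The problem would remain if the child sessions were perfectly matched.

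What is at stake is the wording of the main conclusion for all the standardized primary outcomes.

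**Working it through.** The plan gives no figure on this point, so the main check sets the sections side by side.

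**Step 1. Eligibility for caregiver sessions by the week 6/7 rating (6.3.1, 6.3.2, 4.2, 7.2)**

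| Session | IG1 caregivers | IG2 caregivers |
|---|---|---|
| Pre-intervention meeting | Eligible | Unclear |
| Week 3 | Eligible | Not eligible |
| Week 6 | Eligible | Not eligible |
| Post-intervention meeting | Timing relative to the rating not stated | Unclear |

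The firm difference is two sessions against none. It is a difference in eligibility; attendance is not reported.

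**Step 2. Overlap of content and outcome.** The two sessions cover resilience, coping and classification of behavior. In 7.1.1 the caregivers then rate negative affect, well-being, flexibility, persistence, and emotional and social functioning, among others.

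**Step 3. What the ANCOVA estimates.** Let C be the true difference in child change between arms, and let R1 and R2 be the mean post-baseline shifts in rating for the same behavior. With Y the week-7 mean, X the baseline mean and b the baseline slope, the adjusted difference is

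(Y1 − Y2) − b(X1 − X2).

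R1 and R2 enter Y but not X, because the teaching follows the baseline rating. The expected adjusted difference is therefore C + (R1 − R2). Baseline adjustment removes none of R1 − R2. The other covariate in 8.2.1, maturation seen in IG2's waiting period, does not measure how IG1 caregivers rate.

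**Step 4. Does a larger sample help?** Illustration with assumed values: C = 0, R1 − R2 of 0.2, 0.3 or 0.5 SD in either direction, unadjusted two-sided t-test at 0.05. The group size of 9 lies within the 8-10 of section 8.3; 21 and 35 are future group sizes in 8.1. The chance of a significant result is:

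| Assumed shift (SD) | 9 per group | 21 per group | 35 per group |
|---|---|---|---|
| 0 | 5% | 5% | 5% |
| 0.2 | 7% | 10% | 13% |
| 0.3 | 9% | 16% | 24% |
| 0.5 | 17% | 35% | 54% |

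At the present size the effect on the error rate is small for shifts of 0.2-0.3 SD. It grows with sample size, because a larger study estimates C + (R1 − R2) more precisely and not C.

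**Step 5. Is there another outcome to lean on?** GAS is the only child outcome not completed by caregivers. Under 9.1 it is recorded by research team members, with no masking described, and under 6.1.2 research students help to lead the BRP groups. Section 7.1.1 says the parent-proxy COPM is used mainly to develop the GAS goals. The GAS domains in 7.1.2 are behavior, engagement/participation and resilience, which are not the PedsQL or NIH Toolbox domains. The planned primary GAS contrast in 8.2.2 sets IG1 in weeks 0-7 against IG2 in weeks 7-14, so it is not concurrent. However, 7.1.2 and 7.2 have GAS scored weekly in both arms and in both periods, so a concurrent weeks 0-7 contrast can be computed.

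**The case against.** **The plan may already mean the combined programme.** Section 2.1 asks about the BRP, 2.2 speaks of caregivers taking part in it, and the caregiver component sits under Interventions. This is a natural reading and it stands in part. It settles what the treatment is but not what the outcome is: 2.2 still reads a caregiver rating as a change in the child.

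**Exposure and awareness are partly inferred.** A reader might infer three or four caregiver sessions in IG1 against none in IG2. The documents do not support that. The third line of 6.3.2 restricts only weeks 3 and 6, the line requiring both post-intervention periods is unclear about who attends, and 6.3 mentions participation difficulties. Because the rating is at week 6/7, its order relative to the week 6 session is not fixed either. A reader might also take it as stated that caregivers know the arm. That is a reasonable inference from session attendance and the absence of masking, but no section says it. These points stand; the two-session difference in eligibility is enough.

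**The size is unknown.** It is tempting to express an assumed shift as a share of the effect sizes in 8.1 (d = 0.53 to 0.68). That is not supportable: 8.1 does not say which contrast produced those values, and a downward shift would mean they understate the effect.

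**The design can no longer change.** Sections 5.2 and 8.1 already report enrolment and observed power. This stands, and it confines the remedy to analysis and wording.

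**Conclusion.** The point holds as one of non-separability. The week-7 IG1 versus IG2 difference on every standardized measure combines a change in the child with any change in how IG1 caregivers rate, and baseline adjustment does not separate the two. The size and direction are not given by the documents; the shifts in the illustration are assumptions.

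The conclusion rests on three things: caregivers complete all the standardized forms, no masking is described, and the week 3 and week 6 sessions are closed to IG2 caregivers during Phase 1. It also assumes that at least some IG1 caregivers attended a session before rating.

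A reader might go further and infer that the children did not change, or that a stated fraction of the effect is reporting bias. The documents support neither.

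**What to change.** 1. In 2.1, 2.2 and 8.2.1, define the week-7 standardized-measure result as the effect of the combined child-plus-caregiver programme on caregiver-reported child functioning. State that a change in the child will not be concluded from these measures alone.
2. In 8.2.2, add a concurrent IG1 versus IG2 GAS contrast over weeks 0-7 from the weekly scores already collected, labelled as supportive evidence only. State its limits beside it: scored by research staff with no masking described, goals developed using the parent-proxy COPM, and no coverage of the PedsQL or NIH Toolbox domains.

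The cost is wording, one extra analysis of data in hand and a more modest claim. No new assessment or assessor is needed.

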9.2 Data Storage

- Electronic data stored on password-protected, encrypted servers
- Physical forms stored in locked cabinets in secure research offices
- Data de-identified for analysis using participant ID numbers
- Data retention period: 7 years post-study completion

9.3 Data Quality Assurance

- Regular data monitoring for completeness and accuracy
- Inter-rater reliability checks for GAS observations
- Standardized training for all data collection staff

10. Ethical Considerations

10.1 IRB Approval

Study approved by overseeing institution under IRB-FY2022-23

10.2 Informed Consent Process

- Written informed consent obtained from all parents/caregivers
- Consent process includes study description, risks, benefits, voluntary participation
- Right to withdraw at any time without penalty
- Translation services available as needed

10.3 Risk-Benefit Assessment

Minimal Risks:

- Potential emotional responses during intervention activities
- Breach of confidentiality (mitigated through data security protocols)

Benefits:

- Access to evidence-based trauma-informed intervention
- Potential improvements in self-regulation, behavior, and resilience
- Contribution to research benefiting similar populations

10.4 Participant Safety

- Trained occupational therapy staff monitor for adverse reactions
- Protocols for managing emotional dysregulation during sessions
- Referral pathways for participants needing additional support
- Regular safety monitoring throughout study period

11. Quality Assurance and Monitoring

11.1 Protocol Adherence

- Standardized BRP manual followed for all intervention sessions
- Regular weekly team meetings to review protocol implementation
- Documentation of any protocol deviations

11.2 Staff Training

- All intervention staff trained in BRP protocol delivery
- Training in trauma-informed care approaches
- Regular supervision by licensed occupational therapists
- Inter-rater reliability training for GAS observations across all persons recording data

11.3 Data Monitoring

- Weekly review of attendance and assessment completion
- Monthly data quality checks ([name] and [name])
- Progress reports to funding agencies as required (midterm and final to AOTF)

12. Adverse Event Reporting

12.1 Adverse Event Definitions

- Any negative emotional or behavioral reaction requiring intervention cessation
- Physical injury during intervention activities
- Disclosure of child abuse or neglect requiring mandatory reporting

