12.2 Reporting Procedures

- Immediate documentation of adverse events as required by YWCA site
- Notification of PI within 24 hours
- IRB reporting within required timeframes
- Appropriate referrals for participant safety and support

13. Protocol Amendments

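### Section 12.1 counts an emotional reaction as an adverse event only if it requires cessation, so reactions managed or referred under 10.4 fall outside the 12.2 reporting steps

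*Combined protocol and SAP*

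**What the plan says.** Section 10.3 names two risks. One is "Potential emotional responses during intervention activities", with no severity attached; the other is "Breach of confidentiality (mitigated through data security protocols".

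Section 10.4 has staff watch for adverse reactions, a term it does not define. It also provides "Protocols for managing emotional dysregulation during sessions" and "Referral pathways for participants needing additional support". It does not say that use of either is recorded, or that a child who needs either leaves the programme.

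Section 12.1 gives three adverse event definitions: "Any negative emotional or behavioral reaction requiring intervention cessation", "Physical injury during intervention activities" and "Disclosure of child abuse or neglect requiring mandatory reporting". There is no general category and no wording that leaves the list open.

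Section 12.2 attaches its steps to adverse events: documentation according to site requirements, "Notification of PI within 24 hours", IRB reporting, and referral for safety and support.

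**The concern.** The children are 24 to 66 months old with a history of ACEs (section 2.1), and several weekly themes in 6.1.1 deal directly with emotions and their regulation. An emotional reaction is the harm that the protocol itself foresees. Yet the definition that opens the reporting route starts at cessation, above the two responses that 10.4 provides.

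What is at stake is safety information. A child who is repeatedly dysregulated, is settled each time and stays in the programme produces no adverse event. A child who is referred for more support but continues produces none either, so the 24-hour route does not bring that child to the PI's attention. A later statement that no adverse events occurred would be true under 12.1 and could still be misread as saying that no child needed the protocol or a referral. Section 15.3 plans to make the BRP manual available for clinical use, so readers may rely on such a statement.

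**Working it through.** No formula applies, and the plan states no adverse event rate, count or safety sample size to reproduce. The check sets 10.3, 10.4, 12.1 and 12.2 side by side and follows each kind of occurrence through them.

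| Occurrence | Named in 10.3 | Response in 10.4 | Event under 12.1 | 12.2 steps |
|---|---|---|---|---|
| Reaction settled with the dysregulation protocol, session continues | Yes | Yes | No | No |
| Reaction followed by referral, no session stopped, child continues | Yes | Yes | No | No |
| Reaction ends the child's session, child returns later | Yes | Yes | Only if cessation means the session | Depends on that reading |
| Reaction ends the child's participation | Yes | Yes | Yes | Yes |
| Confidentiality breach | Yes | None stated | No | No |
| Physical injury, or disclosure of abuse or neglect | No | None specific | Yes | Yes |

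1. **Threshold.** Emotional reactions match one of the three definitions, and only at cessation. The first two rows are excluded whichever way cessation is read.

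2. **Undefined term.** The third row turns on the meaning of cessation. If it means the programme, the definition comes close to the withdrawal criterion for child safety concerns in 5.5. If it means the session, it still leaves out every reaction settled in the room. Section 6.1.2 puts 4 to 5 people in each BRP group (1 therapist + 1 capstone student + 2 to 3 research students), and they could classify the same episode differently.

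3. **Referral in two roles.** In 10.4 referral is a pathway that needs no event. In 12.2 it is one of the steps taken after an event. The text does not say whether needing a referral makes the reaction an event.

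4. **Breach.** A confidentiality breach matches none of the three definitions. Section 11.1 documents protocol deviations and could cover it, but does not say so.

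5. **Other routes.** The withdrawal criteria (5.5), data management (9.1 to 9.3), protocol adherence (11.1) and data monitoring (11.3) contain no rule that would record managed or referred reactions as events.

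**The case against.** The strongest reply is that some threshold is reasonable. Section 10.3 speaks of emotional responses, not harmful ones, and a programme that teaches children to identify emotions will evoke them. Nothing in the documents requires every named risk to be an adverse event. This stands against treating every response as an event. It does not answer the case of a reaction serious enough to need the 10.4 protocol or a referral.

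A second reply is that such a child would be noticed. Section 7.1.2 has weekly GAS observations, including a behaviour goal; 9.1 has therapy leads review the scoring; 11.1 has weekly team meetings; and 10.4 promises regular safety monitoring. The dysregulation protocols, whose content is not given, and the site and IRB requirements behind 12.2 may also demand documentation. This stands in part: such a child is less likely to go unseen. But none of these provisions is stated to record, count or escalate the reaction.

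Three stronger readings are tempting and are not supported:

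- A reader might infer that the event count fails as a test of the minimal-risk wording in 10.3. The plan proposes no such test and no adverse event tabulation; the wording is a heading in the ethics section.
- A reader might multiply 38 children by 21 sessions (3 per week × 7 weeks) to get 798 child-sessions and then put a number on missed episodes. The product assumes full attendance, and the documents give no reaction rate to apply to it.
- A reader might infer that a confidentiality breach would go unreported altogether. It is a different kind of incident from a child's reaction, and deviation documentation or IRB rules may cover it. What can be said is that the plan does not state the route.

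**Conclusion.** The point holds as a gap in safety reporting. On the plan's own text, a reaction that needed the dysregulation protocol or a referral, but not cessation, triggers no documentation and no notice to the PI under 12.2. Its size can be given only as a mapping: of the two risks in 10.3, emotional responses are captured only from cessation upwards, and confidentiality breach has no stated reporting route.

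This rests on reading the 12.1 list as closed, since nothing in it suggests otherwise, and on no unseen site rule or session protocol adding a recording duty. If such a rule exists, citing it would close much of the gap.

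The efficacy analysis is unaffected. The point is a cheap improvement and does not threaten the trial's validity. Because 5.2, 8.1 and 8.3 already report achieved enrolment, post-hoc power and analysis sample sizes, prospective recording can no longer be changed in full.

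**What to change.** Reconcile 10.3, 10.4, 12.1 and 12.2:

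- Define cessation in 12.1 as the session, the programme, or both as separate grades.
- For recording only, add a lower tier for reactions that trigger the 10.4 dysregulation protocol or a referral, in both BRP and control periods. State whether the 24-hour notice to the PI applies to that tier.
- State where a confidentiality breach is reported, by the deviation route or the IRB route.
- Where sessions are already complete, check whatever records exist for such episodes, and qualify any statement that no adverse events occurred by the 12.1 threshold.

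How an individual child is managed does not change, and which clinical threshold is right is not judged here.

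The cost is wording in 12.1 and 12.2, a place to record the lower tier, and a search of existing records that may be incomplete. The downsides are a few more minor events to log, a recorded rate above zero, and possibly an IRB amendment under 13.1.

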4.2 Study Design Overview

- Phase 1: Intervention Group 1 (IG1) receives BRP intervention for 7 weeks while Intervention Group 2 (IG2) receives standard care (waitlist control)
- Phase 2: IG2 receives BRP intervention for 7 weeks while IG1 continues standard care activities
- Total study duration: 14 weeks

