6.2 Standard Care Control Condition

Purpose: Control for positive researcher interaction effects while providing beneficial activities

Duration: Concurrent with BRP intervention periods **Content:** School readiness skills supplementing existing curriculum **Weekly Domains:**

- Perceptual motor skills
- Fine motor skills (tool use and coloring)
- Problem solving
- Teamwork and coordination
- Motor planning

Staffing: One licensed occupational therapist

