7.1.2 Goal Attainment Scaling (GAS)

Domains: Three individualized goals per participant

- Behavior
- Engagement/Participation
- Resilience

Scoring: -2 (much worse than expected) to +2 (much better than expected outcome) **Frequency:**

Weekly observations during both intervention and control periods **Conversion:** Raw scores converted to T-scores (M=50, SD=10) for statistical analysis

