8.2 Statistical Methods

8.2.1 Primary Analysis - Standardized Measures

Baseline Comparisons: Independent samples t-tests for continuous variables to assess randomization success

Primary Efficacy Analysis: Analysis of Covariance (ANCOVA)

- Independent Variable: Group assignment (IG1 intervention vs. IG2 waitlist control)
- Dependent Variables: Week 7 standardized assessment scores
- Covariates: Baseline scores, any maturation effects identified in IG2 waitlist period
- Effect sizes: Cohen's d with 95% confidence intervals

Secondary Analysis: Paired samples t-tests for within-group changes

- One-tailed tests for intervention effects (directional hypotheses)
- Two-tailed tests for control period effects

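### Section 12.1 ties distress and injury to 'intervention', so as written such events in control sessions are not reportable and harms are not counted alike by condition

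*Combined protocol and SAP*

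**What the plan says.** Section 12.1 lists three kinds of adverse event:

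1. "Any negative emotional or behavioral reaction requiring intervention cessation"
2. "Physical injury during intervention activities"
3. "Disclosure of child abuse or neglect requiring mandatory reporting"

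Section 12.2 sets out what follows an adverse event: documentation, "Notification of PI within 24 hours", IRB reporting and referral.

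The control condition in Section 6.2 is not passive. A licensed occupational therapist delivers school-readiness activities at the same time as BRP. The content includes "Perceptual motor skills", motor planning and teamwork. Its stated purpose is to control for contact with researchers. Under Section 4.2 each group has 7 weeks of BRP and 7 weeks of the comparator, in opposite order, over 14 weeks.

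Section 10.4 adds general safety monitoring over the study and procedures for dysregulation in sessions. Section 8 contains no analysis of adverse events.

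**The concern.** The first two definitions depend on the word 'intervention'. If that word means BRP, a child who falls during a BRP session has an adverse event, and a child who falls in the same way during a control motor session does not. The PI and IRB steps in Section 12.2 apply to adverse events, so they take over the same limit.

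Two things are at stake. The first is capture: study staff deliver control sessions to preschool children, and distress or injury there could go unreported under the written rule. The second is interpretation. Preschoolers have bumps and upsets in any group activity. If these are recorded under BRP but not under control, a simple table by condition makes BRP look less safe than it is, and background events cannot be separated from events due to the program.

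**Working it through.** The documents give no safety figure (no event rate, safety sample size or safety power), so there is nothing to reproduce. The check is mainly textual.

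**Step 1. Count the restricted definitions.** Distress and injury both contain the word 'intervention'; disclosure does not. That is 2 of 3. The two differ in form. Injury is limited by setting. Distress is limited by consequence, since the intervention must have to stop. If 'intervention' means BRP, the result is the same: a control child has no BRP in progress to stop.

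**Step 2. Establish what 'intervention' means here.**

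- Section 4.2 pairs the BRP intervention in one group with standard care (waitlist control) in the other.
- Section 7.1.2 contrasts the two: "Weekly observations during both intervention and control periods".
- Section 8.2.1 plans one-tailed tests for intervention effects and, separately, "Two-tailed tests for control period effects".
- Section 11.1 requires the BRP manual at every intervention session. Control sessions have different content, so they cannot be intervention sessions in that sense.
- Section 11.2 trains intervention staff to deliver BRP.
- Against these, the heading of Section 6, in the plural, covers BRP, the control condition and the caregiver component, and both arms are named Intervention Group.

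Five places use the word for BRP. The Section 6 heading and the arm names allow something wider.

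**Step 3. Look for text that widens the definition.** Section 10.4 covers monitoring and management and does not say what counts as an adverse event. Section 12.2 refers to site requirements but still applies to adverse events. Neither brings control sessions within the definition.

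**Step 4. Time affected.** 7 control weeks / 14 study weeks = 50% of calendar weeks for each child. This cannot be turned into a share of session exposure. Section 6.1 gives BRP 3 sessions a week of 30 to 45 minutes, but Section 6.2 gives no frequency or length for control.

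**Step 5. Where the asymmetry falls.** This is an illustration. Section 5.2 gives 38 enrolled. Assume 19 per arm (the split is not stated) and the same true probability p, in each condition, that a child has a distress or injury event.

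Within Phase 1, expected BRP children with an event = 19p, and P(at least one) = 1 − (1 − p)^19:

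| Assumed p | Expected, BRP | P(at least one), BRP | Recorded, control (narrow reading) |
|---|---|---|---|
| 5% | 0.95 | 62% | 0 by definition |
| 10% | 1.9 | 87% | 0 by definition |
| 20% | 3.8 | 99% | 0 by definition |

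Over all 14 weeks, each arm has one captured BRP period and one uncaptured control period. The expected recorded count is 19p in both arms, so a total by arm is not tilted.

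**Step 6. What equal capture would gain.** With 19 per arm and two-sided alpha 0.05, power = Φ{[|p1 − p2|√n − 1.96√(2p̄(1 − p̄))] / √(p1(1 − p1) + p2(1 − p2))}. For 5% versus 15%: (0.10 × 4.359 − 1.96 × 0.424) / 0.418 = −0.946, so power is 17%. The same formula gives 40% for 5% versus 25%, and 33% for 10% versus 30%. With 0 events in 19 children, the one-sided 95% upper limit is 1 − 0.05^(1/19) = 14.6%. The gain is fair description, not a powered test.

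**The case against.** The strongest reply is that the narrow reading is not the only one. Section 6 groups BRP, control and caregiver sessions under one heading, so intervention activities could mean anything in that section. On this view there is no gap, only loose wording. The reply stands in part: a reader might infer that a control-session injury is definitely not an adverse event, and the documents do not settle that. But the wider reading sits badly with Sections 4.2, 7.1.2, 8.2.1, 11.1 and 11.2, and a safety definition that staff can read in two ways needs clarifying.

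A second reply is that Section 10.4 already provides study-wide monitoring and that the site may keep its own incident records. Staff may well have noticed and managed control-session events. This weakens any claim that such events were missed in practice. It does not change which events the protocol sends to the PI and IRB.

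A third reply is that no harms comparison is planned and Section 10.3 classes the risks as minimal. That is correct and limits the point to capture and description.

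A reader might also infer that harms cannot be compared between arms, or that every count by arm is biased against BRP. The documents do not support this. Both arms receive both conditions for 7 weeks, so the exclusion falls equally on 14-week totals, and disclosures are comparable throughout. Nor do they support saying that half of session exposure is uncovered, because control session frequency and length are not given.

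**Conclusion.** The point holds as a minor one about safety capture and descriptive reporting. On the reading that best fits the rest of the document, two of three adverse-event definitions leave out the control condition, which takes up 7 of each child's 14 study weeks. Descriptions by condition, or by group within Phase 1, would then compare a recorded BRP count with a control count that is zero by definition for distress and injury.

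This rests on reading 'intervention' as BRP, which the wording favours but does not settle. The counts in the illustration rest on an assumed 19 per arm and assumed event rates of 5% to 20%; they show direction and rough scale only. No planned analysis is affected.

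**What to change.** In Section 12.1, replace the intervention restriction with *any study session (BRP, control, caregiver or joint session, or assessment)*. Section 6.3 already calls the caregiver sessions an intervention component; listing them removes doubt. Record group and phase for each event, and report counts by condition and phase, without a formal test.

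The text change is one sentence, plus group and phase on the event form. The downside is slightly more events to log.

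The wording change cannot recover events that were never recorded. Section 5.2 gives an achieved enrolment of 38 and a final analytic sample of 32, and Section 8.3 gives realised sample sizes, so data collection may already be complete. In that case, check site incident records for control-session events and include them by condition and phase, or state in the report that control-session distress and injury were not captured.
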